FSH	follicle-stimulating hormone
FVC	forced vital capacity
G6PD	glucose-6-phosphate dehydrogenase
GCP	Good Clinical Practice
GLI	Global Lung Function Initiative
GPS	Global Patient Safety (Vertex)
HBE	human bronchial epithelial (cells)
HIPAA	Health Insurance Portability and Accountability Act
HR	heart rate
IA	interim analysis
ICF	informed consent form

Abbreviation	Term
ICH	International Council for Harmonisation
IDMC	independent data monitoring committee
IEC	independent ethics committee
IPD	important protocol deviation
IRB	institutional review board
IVA	ivacaftor (VX-770)
IWRS	interactive web response system
LLN	lower limit of normal
LUM	lumacaftor (VX-809)
MCP	multiple comparisons procedure
MedDRA	Medical Dictionary for Regulatory Activities
MMRM	mixed-effects model for repeated measures
OATP1B1	organic anion transporting polypeptide 1B1
PD	pharmacodynamic, pharmacodynamics
PE	physical examination
PI	pancreatic insufficiency
PK	pharmacokinetics
ppFEV ₁	percent predicted forced expiratory volume in 1 second
PR	PR interval
q12h	every 12 hours
qd	daily
QRS	portion of an ECG comprising the Q, R, and S waves, together representing ventricular depolarization
QTc	QT interval corrected
QTcB	QT interval corrected by Bazett's formula
QTcF	QT interval corrected by Fridericia's formula
RR	interval from the onset of 1 QRS complex to the next
SAE	serious adverse event
SAP	statistical analysis plan
SD	standard deviation
SE	standard error
SI	International System
SUSAR	suspected, unexpected, serious adverse reaction
SwCl	sweat chloride
TBD	to be determined
TC	triple combination
TE	treatment emergent
TEAE	treatment-emergent adverse event
TEZ	tezacaftor (VX-661)
ULN	upper limit of normal
US	United States
UV	ultraviolet

5 INTRODUCTION

5.1 Background

Cystic fibrosis (CF) is an autosomal recessive chronic disease with serious morbidities and frequent premature mortality. At present, there is no cure. CF affects approximately 70,000 individuals worldwide¹ (approximately 30,000 in the US^{1,2} and 32,000 in the European Union³). Based on its prevalence, CF qualifies as an orphan disease.^{4,5}

CF is caused by reduced quantity and/or function of the CFTR protein due to mutations in the *CFTR* gene. The CFTR protein is an epithelial chloride channel that aids in regulating salt and water absorption and secretion and pH balance in sweat glands and multiple organs, including the lungs, pancreas, and other gastrointestinal organs. Despite progress in the treatment of CF with antibiotics and mucolytics, the predicted median age of survival for a person with CF is approximately 40 years.^{2,6} Progressive loss of lung function is the leading cause of mortality.⁷ More effective treatments are needed for CF.

More than 2000 mutations of the *CFTR* gene have been identified.⁸ Most of these mutations are not associated with CF disease or are very rare. Currently, the CFTR2 database contains information on only 322 of these identified mutations, with sufficient evidence to define 281 mutations as disease-causing.⁹ The most common disease-causing *CFTR* mutation, *F508del*, accounts for 70% of the identified alleles in people with CF, with nearly half of all people with CF are homozygous for *F508del*.

Based on the understanding of the molecular defects caused by *CFTR* mutations, 2 complementary approaches have been developed to address the decreased quantity and/or function of CFTR in order to enhance chloride transport in patients with CF. Correctors facilitate the cellular processing and trafficking to increase the quantity of functional CFTR at the cell surface. Potentiators increase the channel open probability of the CFTR protein delivered to the cell surface to enhance ion transport. Depending on the amount of residual CFTR channel activity in the membrane, and the pathophysiology of that activity (reflecting the *CFTR* genotype of the patient and possibly other factors), both approaches may be required.

The therapeutic activity of CFTR correctors and potentiators has been established with products that were developed by Vertex and approved for the treatment of CF: ivacaftor (IVA) monotherapy (Kalydeco[®]), and lumacaftor (LUM) in combination with IVA (Orkambi[®]). Kalydeco and Orkambi are approved to treat CF in patients with specific *CFTR* genotypes. Tezacaftor (TEZ; VX-661) is a first-generation CFTR corrector that improves the processing and trafficking of the F508del-CFTR protein, resulting in an increase in the quantity of F508del-CFTR protein at the cell surface. IVA increases the open-channel probability of the F508del-CFTR protein that has been delivered to the cell surface by TEZ, thereby enhancing total chloride transport. The combined effect of TEZ and IVA is increased quantity and function of F508del-CFTR at the cell surface.

VX-659 is a next-generation CFTR corrector. In vitro, VX-659 improves the processing and trafficking of F508del-CFTR, thereby increasing the quantity of functional F508del-CFTR protein at the cell surface.¹⁰ The effect of VX-659 was additive to the effect of TEZ. The CFTR protein delivered to the cell surface by VX-659 alone or in combination with TEZ (VX-659/TEZ) was potentiated by IVA.¹⁰ In human bronchial epithelial (HBE) cells studied in vitro, the triple combination (TC) of VX-659, TEZ, and IVA (VX-659/TEZ/IVA) increased CFTR chloride transport more than any of the dual combinations (VX-659/TEZ, VX-659/IVA, and TEZ/IVA) or individual components (VX-659, TEZ, and IVA) under most conditions studied.¹⁰

VX-561 (also known as CTP-656 and C-10355) is a deuterated isotope of IVA with a specific pattern of 9 substituted deuteriums. In vitro data indicate similar potency of VX-561 in HBE cells relative to IVA.¹¹ Safety pharmacology and nonclinical toxicology studies of VX-561 demonstrate a similar safety profile relative to IVA. Phase 1 clinical studies in healthy subjects have shown that VX-561 had a reduced rate of clearance, increased exposure, greater plasma levels at 24 hours, and a longer half-life compared to IVA, thereby supporting once daily dosing.

5.2 Rationale for This Study

This is the second clinical study of VX-659 and is designed to evaluate the safety and efficacy of VX-659 in TC with TEZ and either IVA or VX-561 in subjects with CF who are heterozygous for *F508del* with a second *CFTR* allele carrying a minimal function (MF) mutation that is not expected to respond to TEZ, IVA, or TEZ/IVA (F/MF genotypes) and homozygous for *F508del* (F/F genotype).

Data from nonclinical studies of VX-659, TEZ, IVA, and VX-561 and the current unmet medical need for new treatments for CF support clinical development of VX-659 in combination with other CFTR modulators for the treatment of CF.

6 STUDY OBJECTIVES

6.1 Primary Objectives

Parts 1 and 2: To evaluate the safety and tolerability of VX-659 in TC with TEZ and IVA

Part 3 (optional): To evaluate the safety and tolerability of VX-659 in TC with TEZ and VX-561

All parts: To evaluate the efficacy of VX-659 in TC with TEZ and either IVA or VX-561

6.2 Secondary Objectives

Parts 1 and 2: To evaluate the pharmacodynamic (PD) effects of VX-659 in TC with TEZ and IVA on CFTR function

Part 3 (optional): To evaluate the PD effects of VX-659 in TC with TEZ and VX-561 on CFTR function

All parts:

- To evaluate the pharmacokinetics (PK) of VX-659 when administered in TC with TEZ and either IVA or VX-561
- To evaluate the PK of TEZ, IVA, VX-561 and their respective metabolites when administered with VX-659 (as applicable)

7 STUDY ENDPOINTS

7.1 Primary Endpoints

- Safety and tolerability assessments based on adverse events (AEs), clinical laboratory values, standard 12-lead ECGs, vital signs, and pulse oximetry
- Absolute change in percent predicted forced expiratory volume in 1 second (ppFEV₁) from baseline through the Day 29 Visit

7.2 Secondary Endpoints

- Absolute change in sweat chloride concentrations from baseline through the Day 29 Visit
- Relative change in ppFEV₁ from baseline through the Day 29 Visit
- Absolute change in Cystic Fibrosis Questionnaire-Revised (CFQ-R) respiratory domain score from baseline at the Day 29 Visit
- PK parameters of VX-659, TEZ, M1-TEZ, IVA, M1-IVA, and VX-561

8 STUDY POPULATION

Eligibility will be reviewed and documented by an appropriately qualified member of the investigator's team before subjects are randomized (Part 1 and Part 3) or receive TEZ/IVA in the Run-in Period (Part 2).

8.1 Inclusion Criteria

1. Subject will sign and date an informed consent form (ICF).
2. Willing and able to comply with scheduled visits, treatment plan, study restrictions, laboratory tests, contraceptive guidelines, and other study procedures.
3. Subjects will be aged 18 years or older on the date of informed consent.
4. Body weight ≥ 35 kg.
5. Subjects must be able to produce a valid (quantity-sufficient) sweat sample at screening. If the initial screening collection results in insufficient sweat volume, then the sweat chloride collection may be repeated once, after approval by the medical monitor.
 - Parts 1 and 3: Subjects must have a sweat chloride value ≥ 60 mmol/L at screening or documented in the form of a laboratory report in the subject's medical record. If the sweat chloride value cannot be determined from the screening test for a reason other than insufficient sweat volume (i.e., because of laboratory error, damaged specimen, or equipment malfunction), it is acceptable to use a sweat chloride value that was obtained before previous treatment with IVA, LUM/IVA, or an investigational CFTR modulator.
 - Part 2: For subjects with a sweat chloride value ≥ 60 mmol/L at screening or documented in the form of a laboratory report in the subject's medical record, medical monitor approval is not required. For subjects with a sweat chloride value < 60 mmol/L at screening and no documented historical value ≥ 60 mmol/L, medical monitor approval is required based on documented evidence of chronic sinopulmonary disease manifested by at least 1 of the following:

- Persistent colonization/infection with typical CF pathogens, including but not limited to, *Staphylococcus aureus*, *Haemophilus influenzae*, and/or *Pseudomonas aeruginosa*
 - Chronic cough and sputum production
 - Persistent chest radiograph abnormalities (e.g., bronchiectasis, atelectasis, infiltrates, hyperinflation)
 - Nasal polyps, chronic sinusitis, or radiographic or computed tomographic abnormalities of the paranasal sinuses
6. Subjects must have an eligible *CFTR* genotype as noted below. If the screening *CFTR* genotype result is not received before randomization, a previous *CFTR* genotype laboratory report may be used as a source document to establish eligibility and avert the risk of screening period expiration. Note: Subjects who have been randomized and whose screening genotype does not confirm study eligibility must be discontinued from the study (Section 9.10).
- Part 1 and Part 3: Heterozygous for *F508del* with a second *CFTR* allele carrying an MF mutation that is not expected to respond to TEZ, IVA, or TEZ/IVA (Appendix A)
 - Part 2: Homozygous for *F508del*
7. FEV₁ value $\geq 40\%$ and $\leq 90\%$ of predicted mean for age, sex, and height (equations of the Global Lung Function Initiative [GLI])¹² at the Screening Visit. Spirometry measurements must meet American Thoracic Society/European Respiratory Society criteria¹³ for acceptability and repeatability.
8. Stable CF disease as judged by the investigator.
9. Willing to remain on a stable CF treatment regimen through the planned end of treatment or, if applicable, the Safety Follow-up Visit.

8.2 Exclusion Criteria

1. History of any comorbidity that, in the opinion of the investigator, might confound the results of the study or pose an additional risk in administering study drug to the subject.
2. History of clinically significant cirrhosis with or without portal hypertension.
3. Risk factors for Torsade de Pointes, including but not limited to, history of any of the following: familial long QT syndrome, chronic hypokalemia, heart failure, left ventricular hypertrophy, chronic bradycardia, myocardial infarction, cardiomyopathy, history of arrhythmia (ventricular or atrial fibrillation), obesity, acute neurologic events (subarachnoid hemorrhage, intracranial hemorrhage, cerebrovascular accident, or intracranial trauma), or autonomic neuropathy.
4. Current or past history of peptic ulcer disease.
5. History of hemolysis.
6. Glucose-6-phosphate dehydrogenase (G6PD) deficiency, defined as G6PD activity less than the lower limit of normal (LLN) or 70% of the mean of the LLN and the upper limit of normal (ULN), whichever is greater.

7. Any of the following abnormal laboratory values at screening:
 - Hemoglobin <10 g/dL
 - Total bilirubin $\geq 2 \times$ ULN
 - Aspartate transaminase (AST), alanine transaminase (ALT), gamma-glutamyl transpeptidase, or alkaline phosphatase $\geq 3 \times$ ULN
 - Abnormal renal function defined as glomerular filtration rate ≤ 50 mL/min/1.73 m² (calculated by the Modification of Diet in Renal Disease Study Equation)^{14, 15}
8. An acute upper or lower respiratory infection, pulmonary exacerbation, or changes in therapy (including antibiotics) for sinopulmonary disease within 28 days before the first dose of study drug.
9. Lung infection with organisms associated with a more rapid decline in pulmonary status (e.g., *Burkholderia cenocepacia*, *Burkholderia dolosa*, and *Mycobacterium abscessus*). For subjects who have had a history of a positive culture in the past, the investigator will apply the following criteria to establish whether the subject is free of infection with such organisms:
 - The subject has had 2 respiratory tract cultures negative for these organisms within the 12 months before the screening visit, with no subsequent positive cultures.
 - These 2 respiratory tract cultures were separated by at least 3 months, and 1 of them was obtained within 6 months before the screening visit.
10. An acute illness not related to CF (e.g., gastroenteritis) within 14 days before the first dose of study drug.
11. A standard digital ECG demonstrating QTc >450 msec at screening. If QTc exceeds 450 msec for the screening ECG, the ECG should be repeated 2 more times during the Screening Period, and the subject will be excluded if the average of the 3 QTc values is >450 msec. Study sites should use QTcF unless they receive approval in advance from the medical monitor to use QTcB (Section 11.7.5).
12. History of solid organ or hematological transplantation.
13. History of alcohol or drug of abuse in the past year, including but not limited to, cannabis, cocaine, and opiates, as deemed by the investigator.
14. Ongoing or prior participation in a study of an investigational treatment other than a CFTR modulator within 28 days or 5 terminal half-lives (whichever is longer) before screening. The duration of the elapsed time may be longer if required by local regulations.
15. Use of prohibited medications as defined in Table 9-3, within the specified window before the first dose of study drug.
16. Pregnant or nursing females. Females of childbearing potential must have a negative pregnancy test at screening and the Day 1 Visit (Part 1 and Part 3) or Day -28 Visit (Part 2).
17. The subject or a close relative of the subject is the investigator or a subinvestigator, research assistant, pharmacist, study coordinator, or other staff directly involved with the conduct of

the study. An adult (aged 18 years or older) who is a relative of a study staff member may be randomized in the study provided that

- the adult lives independently of and does not reside with the study staff member, and
- the adult participates in the study at a site other than the site at which the family member is employed.

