9.9 Stopping Rules

Subjects with new treatment-emergent ALT or AST elevations of $>3 \times \text{ULN}$, or total bilirubin $>2 \times \text{ULN}$, must be followed closely, including confirmatory testing performed by the central laboratory within 48 to 72 hours of the initial finding and subsequent close monitoring of ALT, AST, and bilirubin levels, as clinically indicated.

If a subject cannot return to the site for confirmatory testing, a local laboratory may be used. Local laboratory results must be reported immediately to the medical monitor, and the subject must have the tests repeated and sent to the central laboratory as soon as possible (ideally within 48 to 72 hours).

Study drug administration **must be interrupted** immediately (prior to confirmatory testing), and the medical monitor must be notified, if any of the following criteria are met:

- ALT or AST $>8 \times \text{ULN}$
- ALT or AST $>5 \times \text{ULN}$ for more than 2 weeks
- ALT or AST $>3 \times \text{ULN}$, in association with total bilirubin $>2 \times \text{ULN}$ and/or clinical jaundice
- Indirect bilirubin $>2 \times \text{ULN}$ (defined as ULN for total bilirubin minus ULN for direct bilirubin)

A thorough investigation of potential causes should be conducted, and the subject should be followed closely for clinical progression.

Study drug administration **must be discontinued**, if either of the following criteria is met:

- Subsequent ALT or AST values confirm the initial elevation that satisfied the interruption rule (above), and no convincing alternative etiology (e.g., acetaminophen use, viral hepatitis, or alcohol ingestion) is identified, regardless of whether transaminase levels have improved
- Subsequent indirect bilirubin values confirm the initial value as $>2 \times \text{ULN}$ (defined as ULN for total bilirubin minus ULN for direct bilirubin), in association with decreased haptoglobin

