If an alternative, reversible cause of transaminase elevation and/or increased bilirubin or clinical jaundice has been identified, study drug administration may be resumed once transaminases or bilirubin return to baseline or are $\leq 2 \times \text{ULN}$, whichever is higher. Approval of the medical monitor is required before resumption of study drug. Upon resumption of study drug, transaminases and bilirubin should be assessed weekly for 4 weeks. If a protocol-defined transaminase or bilirubin elevation interruption threshold recurs during Period 1 or Period 2 (with confirmation of the initial elevation by repeat testing within 48 to 72 hours), then study drugs must be permanently discontinued, regardless of the presumed etiology.

All subjects in whom treatment is discontinued for elevated transaminases and/or bilirubin should have these levels monitored closely until levels normalize or return to baseline.

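### Exclusion 7 limits only total bilirubin, so an eligible subject can already meet the Section 9.9 indirect-bilirubin interruption criterion at screening

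*Protocol*

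**What the plan says.** **Entry.** Protocol 8.2, exclusion 7, bars a screening value of "Total bilirubin $\geq 2 \times$ ULN". It also bars "Aspartate transaminase (AST), alanine transaminase (ALT), gamma-glutamyl transpeptidase, or alkaline phosphatase" at or above 3×ULN. Nothing in 8.1 or 8.2 limits indirect bilirubin.

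**Interruption.** Protocol 9.9 stops dosing "immediately (prior to confirmatory testing), and the medical monitor must be notified, if any of the following criteria are met". The list has four entries. Three need ALT or AST above 3×ULN or higher. The fourth is indirect bilirubin above 2×ULN, with that ULN "defined as ULN for total bilirubin minus ULN for direct bilirubin".

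**Baseline wording.** The opening sentence of 9.9, on close follow-up, begins "Subjects with new treatment-emergent ALT or AST elevations of" and goes on to total bilirubin above 2×ULN. The interruption list does not repeat the treatment-emergent qualifier.

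**After interruption.** Discontinuation on indirect bilirubin needs a confirmed value "in association with decreased haptoglobin". On restarting, 9.9 says: "If an alternative, reversible cause of transaminase elevation and/or increased bilirubin or clinical jaundice has been identified, study drug administration may be resumed". The level required is baseline or at most 2×ULN, whichever is higher, and the medical monitor must approve.

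**The concern.** A stopping threshold normally lies beyond the entry limit, so that crossing it tells the site something has changed on drug. Here one of the four interruption thresholds lies inside the eligible range. A site could enrol a subject correctly, dose, and then have to interrupt because of a value that was present at entry.

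Two things would follow for that subject. The interruption would carry no information about the drug. The route back to dosing would also be unclear, because 9.9 ties resumption to an alternative, reversible cause, and a stable, non-hemolytic elevation may have none. Sites could resolve this differently.

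**Working it through.** There is no figure in the plan to reproduce. The check compares two thresholds.

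**Inputs from the documents.** Eligible if total bilirubin < 2×ULN total (8.2, exclusion 7). Interrupt if indirect bilirubin > 2×(ULN total − ULN direct) (9.9). Total and direct bilirubin are both in the chemistry panel (Table 11-2), so indirect = total − direct.

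**Algebra.** Write T for ULN total, D for ULN direct and d for the subject's direct bilirubin. Both conditions hold when

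2(T − D) + d < total < 2T.

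This range is non-empty whenever d < 2D, which includes every subject with normal direct bilirubin. In units of T it starts at 2 − (2D − d)/T and ends at 2.0. The ULNs change its width but never remove it.

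**Numbers.** The documents give no ULNs, so those below are assumptions (mg/dL).

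| T | D | Indirect limit 2(T − D) | Band start, d = D | Band start, d = 0.1 |
|---|---|---|---|---|
| 1.0 | 0.2 | 1.6 | 1.80×ULN | 1.70×ULN |
| 1.0 | 0.4 | 1.2 | 1.60×ULN | 1.30×ULN |
| 1.2 | 0.3 | 1.8 | 1.75×ULN | 1.58×ULN |
| 1.3 | 0.2 | 2.2 | 1.85×ULN | 1.77×ULN |
| 1.3 | 0.4 | 1.8 | 1.69×ULN | 1.46×ULN |

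Over T from 1.0 to 1.3, D from 0.2 to 0.4 and d from 0.1 up to D, the start runs from 1.30 to 1.85×ULN. A higher d narrows the band: with T = 1.2, D = 0.2 and d at 1.5 times its ULN, it starts at 2 − (0.4 − 0.3)/1.2 = 1.92×ULN.

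**One subject.** T = 1.2, D = 0.3, total 2.2, direct 0.3. Total is 2.2/1.2 = 1.83×ULN, so the subject is eligible. Indirect is 2.2 − 0.3 = 1.9, above 2(1.2 − 0.3) = 1.8, so the interruption criterion is met.

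**The other three criteria.** They need ALT or AST above 8×ULN, above 5×ULN for more than 2 weeks, or above 3×ULN with raised total bilirubin or jaundice. Exclusion 7 bars ALT or AST at 3×ULN or more, so none can be met at screening.

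**When it would surface.** Assessments are predose unless noted (footnote a of Tables 3-1 to 3-3). The first scheduled on-drug chemistry is therefore Day 15 in Parts 1 and 3. In Part 2 it is Day 1, after four weeks of TEZ/IVA.

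**Resumption.** An unchanged value already satisfies the level test, because it equals baseline. The unmet condition is the identified reversible cause.

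**Check on the definition.** If the ULN in the fourth criterion meant the total ULN, the overlap would vanish, since indirect ≤ total < 2T. Section 9.9 defines it otherwise.

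**The case against.** The strongest reply is that 9.9 should be read as a whole. It opens with new treatment-emergent elevations. The reference to confirmatory testing in the interruption sentence points back to that opening, and the resumption level is relative to baseline. On that reading an unchanged screening value triggers nothing. This is a fair reading and may be the intended one. But the interruption list is a separate instruction under which any one criterion suffices, and it does not carry the qualifier. A careful site could read it either way.

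A second reply is that the difference may be deliberate. The pairing with haptoglobin, and exclusions 5 (history of hemolysis) and 6 (G6PD deficiency), suggest that the criterion guards against hemolysis, where a low threshold is defensible. Part of the G6PD rationale in 9.3.4 is redacted, so the public text cannot settle this. Even so, a threshold already exceeded at entry cannot signal a change on drug.

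Third, safeguards exist. The medical monitor is notified at interruption and can see the screening value, restarting is discretionary, and exclusions 1, 5 and 6 may remove some of these subjects. All of that stands and limits the consequence. None of it sets an indirect-bilirubin limit.

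**Conclusion.** The overlap holds for any direct ULN above zero. It matters only if a subject in the band enrols and the interruption list is read as written. The documents give neither the ULNs nor a frequency. With T = 1.2, D = 0.3 and direct at its ULN, the band is the top 0.25×ULN of the eligible range. Severity is minor.

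A reader might infer more than the documents support:

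- **Forced discontinuation.** The indirect-bilirubin rule requires a confirmed value together with decreased haptoglobin, so a stable, non-hemolytic elevation does not meet it.
- **A fixed loss of two or three dosing days.** The 48 to 72 hour clock belongs to the close-follow-up sentence, which covers ALT or AST elevations and total bilirubin above 2×ULN. This subject's total is below that, and no rule grants resumption on confirmation alone.
- **Permanent discontinuation under the recurrence rule.** A value that never fell has not plainly recurred.
- **An effect on arm means.** Without a frequency, none can be shown.

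**What to change.** Add one line to exclusion 7: indirect bilirubin > 2×ULN at screening, where ULN is the ULN for total bilirubin minus the ULN for direct bilirubin. Entry and interruption then use the same threshold. The value is computed from the total and direct bilirubin already in the panel, so the change needs an amendment line and no new sample.

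The cost is a few otherwise eligible subjects, whom 9.9 as written would interrupt anyway. Protocol 9.1.1.1 already lets an exclusionary liver function result be retested once within 14 days with medical monitor approval, which softens the loss.

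The line acts on the screening value only, so a subject just under the limit can still cross it later. To illustrate, assume normal within-subject variation with CV c around a usual level of x times the limit. The chance of exceeding the limit on one panel is 1 − Φ((1 − x)/(c·x)). At x = 0.90 this is 13% for c = 0.10 and 33% for c = 0.25. At x = 0.75 it is below 0.1% and 9%. These CVs are assumptions.

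Qualifying the indirect-bilirubin criterion in 9.9 as new treatment-emergent, with a stated rise over baseline, would also remove the overlap. It loosens a safety rule, so that choice belongs to the safety physicians.
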